9.2.2 Treatment Compliance

9.2.2.1 Investigational drug and comparative drug (MT-5547 and MT-5547 placebos)

The stipulated dosage and administration, treatment period, and administration method of the investigational drug or comparative drug will not change. The (sub)investigator will administer the investigational drug or comparative drug subcutaneously at the study site at each scheduled subject visit. Subjects will be monitored closely at the study site for 30 minutes after the administration of the investigational drug. The (sub)investigator or a study support staff member will record in the case report form the date and time of administration and location of administration at each subject visit from baseline on.

The administration of the investigational drug by the subject by self-injection will be done at the study site. The (sub)investigator will make sure that the subject properly administers the investigational drug subcutaneously, and the (sub)investigator or a study support staff member will record the date and time and location of administration of the self-injection in the case report form.

9.2.2.2 Control Drugs (Naproxen Tablets and Naproxen Placebo Tablets)

The (sub)investigator or a study support staff member will at each visit during the control drug treatment period check the subject's treatment compliance by questioning the subject and checking the amount of remaining drug. The (sub)investigator or a study support staff member will record in the case report form the dosing regimen of the control drug.

9.2.2.3 Rescue Drug

The dose of the rescue drug (acetaminophen) may not exceed the maximum permitted dose. The (sub)investigator or study support staff member will record the number of days the rescue drug was taken and the amount of rescue drug taken (number of tablets) in the case report form based on the treatment diary (see Attachment 4, "Rescue Drug Treatment Diary"). The (sub)investigator or a study support staff

member will recover the remaining drugs at baseline, Weeks 2, 4, 8, 12, 16, 20, 24, 28, 32, 36, 40, 44, 48, and at treatment period discontinuation and will investigate the subject's treatment compliance and instruct the patient in how to take the rescue drug appropriately and in how to record the information appropriately in the treatment diary.

9.2.3 Efficacy Endpoints

9.2.3.1 Efficacy Assessment Procedures

As much as possible, the efficacy endpoints will be assessed each time in the same order and at the same location.

9.2.3.1.2 Patient's Global Assessment (PGA) of Osteoarthritis

The (sub)investigator or a study support staff member will ask the subject to complete Attachment 6, "PGA," at screening, baseline, Weeks 1, 2, 4, 8, 12, 16, 20, 24, 28, 32, 36, 40, 44, 48, 52, 60, and 68, and at treatment period discontinuation or post-treatment period discontinuation, and will recover Attachment 6 from the subject once the subject has filled it out. The (sub)investigator or a study support staff member will check the information, and if any revisions have been made will confirm the revisions that have been made by the subject and then enter the information in the case report form.

The patient's global assessment is a measure whereby the patient assesses global improvement in osteoarthritis using the following 5-level scale.

1. Much improved
2. Improved
3. No change
4. Worse
5. Much worse

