5.3 Methods of Blinding and Randomization

5.3.1 Method of Blinding

5.3.2 Randomization and Allocation Methods

5.4 Endpoints

5.4.1 Efficacy Endpoints

- (1) Primary efficacy endpoint
WOMAC pain score (change from baseline at Week 16)
- (2) Key secondary efficacy endpoint
WOMAC physical function score (change from baseline at Week 16)

(3) Secondary efficacy endpoints

- 1) Patient global assessment (PGA) (change from baseline at each assessment time point)
- 2) WOMAC pain score (change from baseline at each assessment time point)
- 3) WOMAC physical function score (change from baseline at each assessment time point)
- 4) WOMAC stiffness score (change from baseline at each assessment time point)
- 5) WOMAC total score (change from baseline at each assessment time point)
- 6) Proportions of subjects with 30% and 50% improvements in their WOMAC pain scores compared to baseline (Weeks 16 and 24)
- 7) Proportions of subjects with 30% and 50% improvements in their WOMAC physical function scores compared to baseline (Weeks 16 and 24)
- 8) Numerical Rating Scale (NRS) score for the mean pain on walking in the evaluated joint (change from baseline at each assessment time point)
- 9) SF-36 (change from baseline at each assessment time point)
- 10) EQ-5D-5L (change from baseline at each assessment time point)
- 11) Improvement rate based on the Outcome Measures in Rheumatology Arthritis Clinical Trials-Osteoarthritis Research Society International (OMERACT-OARSI) criteria (at Weeks 16 and 24)
- 12) Amount of rescue medication used (number of days on which rescue medication was used, and amount [number of tablets] used)

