9.2.3.1.6 OMERACT-OARSI

The WOMAC pain subscore and physical function subscore and the PGA will be used to calculate the improvement rate based on the OMERACT-OARSI criteria.

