10.1 Efficacy

For details, see "9.2.3 Efficacy Endpoints."

- (1) Primary efficacy endpoint
WOMAC pain score (change from baseline at Week 16)
- (2) Key secondary efficacy endpoint
WOMAC physical function score (change from baseline at Week 16)
- (3) Secondary efficacy endpoint
 - 1) Patient Global Assessment (PGA) (change from baseline at each assessment time point)
 - 2) WOMAC pain score (change from baseline at each assessment time point)
 - 3) WOMAC physical function score (change from baseline at each assessment time point)
 - 4) WOMAC stiffness score (change from baseline at each assessment time point)
 - 5) WOMAC global score (change from baseline at each assessment time point)
 - 6) Proportions of subjects exhibiting improvements of 30% and 50% in the WOMAC pain score compared to baseline (Weeks 16 and 24)

- 7) Proportions of subjects exhibiting improvements of 30% and 50% in the WOMAC physical function score compared to baseline (Weeks 16 and 24)
- 8) Numerical rating scale (NRS) score for the average pain on walking in the evaluated joint each day (change from baseline at each assessment time point)
- 9) SF-36 (change from baseline at each assessment time point)
- 10) EQ-5D-5L (change from baseline at each assessment time point)
- 11) Percent improvement based on the OMERACT-OARSI criteria (Weeks 16 and 24)
- 12) Rescue medication dose (number of days taken, and amount (number of tablets) taken)

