The robustness of the results of the primary analysis for the effect of the missing mechanism will be checked using a placebo multiple imputation method and a pattern mixing model (including a shift parameter analysis)³⁶⁾ that assumes a missing not at random missing mechanism. A more detailed description of the analysis method will be presented in the SAP.

• Supplementary analysis with respect to the data pooling on 1 mg q4w and placebo

The data on 1 mg q4w and placebo obtained before and after the protocol amendment (Ver. 04.00.00000) will be analyzed using the same method as for the primary analysis to confirm the data homogeneity and the robustness of the results of the primary analysis. Also, homogeneity in demographic and other baseline characteristics [Section 13.3.1] between data obtained before and after the protocol amendment will be confirmed.

(2) Analysis of the key secondary efficacy endpoint

Analyses similar to those described in primary analysis (a) will be performed for the change in the WOMAC physical function score and the change in the PGA from baseline to Week 16, the key secondary efficacy endpoint.

Because this study is a confirmatory study, in order to keep the family wise type 1 error rate to a significance level of 5% (alpha), two-sided, in the tests of the following hypotheses regarding the primary endpoint and the key secondary efficacy endpoint, a gatekeeping method³⁷⁾ based on a graphical approach will be used to perform multiplicity adjustment, as shown in Figure 13.3.2.1 to verify the hypotheses.

This multiplicity adjustment will only be performed for the statistical analyses of data from the double-blind period from screening to Week 16 after treatment initiation.

- Null hypothesis H01: The change from baseline in the WOMAC pain subscale at Week 16 in the 1 mg SC q4w group is the same as that in the placebo group
- Null hypothesis H02: The change from baseline in the WOMAC pain subscale at Week 16 in the 1 mg SC q8w group is the same as that in the placebo group
- Null hypothesis H03: The change from baseline in the WOMAC physical subscale at Week 16 in the 1 mg SC q4w group is the same as that in the placebo group
- Null hypothesis H04: The change from baseline in the WOMAC physical subscale at Week 16 in the 1 mg SC q8w group is the same as that in the placebo group

[figure not shown]

Figure 13.3.2-1: MT-5547 Multiple Test Procedure

(3) Analysis of Secondary Endpoints

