The same method as that described in (a) Primary Analysis will be used to analyze the changes from baseline at each assessment time point in the WOMAC pain score, the WOMAC physical function score, the WOMAC stiffness score, the WOMAC total score, PGA, the NRS score for the average pain on walking in the evaluated joint over the past 24 hours, the SF-36, and the EQ-5D-5L.

A generalized linear mixed-effects model by logit type for response variable with baseline as a covariate and treatment group, K-L grade (2-3 or 4), and evaluated joint location (knee or hip) as factors will be used to evaluate the proportions of subjects achieving 30% and 50% improvements in their WOMAC pain scores at Weeks 16 and 24 compared to baseline as well as the OMERACT-OARSI response rate. A detailed description of this model is presented in the SAP.

The analysis methods used for the other secondary endpoints will be described in the SAP.

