7.1.2.7. Response rate based on the OMERACT-OARSI criteria

Note that the criteria in the diagram above are based on standardized score between 0 and 100. For this study, WOMAC pain and physical function subscale score are between 0 and 10, so the absolute change required for response is the required change in the diagram above divided by 10; PGA is 1, 2, 3, 4 or 5, so the absolute change required for response is at least 1 point.

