8.2.3. Other Efficacy Endpoints

WOMAC pain subscale score, WOMAC physical function subscale score, WOMAC stiffness subscale score, WOMAC total score , WOMAC individual score and PGA

For the changes from baseline at each visit in the WOMAC pain subscale score, the WOMAC physical function subscale score, the WOMAC stiffness subscale score, the WOMAC total score, WOMAC individual score and PGA, the same primary analysis method (MMRM) described in Section 8.2.1 will be analyzed. And the WOMAC pain subscale score will also be summarized at each visit by treatment group on the FAS population. In addition,

change from baseline to week 16 in WOMAC pain subscale score, WOMAC physical function subscale score and PGA will be graphed by visit.

Weekly average and daily walking index joint pain using NRS

For the change from baseline in the weekly average and daily walking index joint pain using NRS, the same primary analysis method (MMRM) described in Section 8.2.1 will be analyzed. In addition, change from baseline to week 16 in weekly average walking index joint pain using NRS will be graphed by visit.

SF-36 / EQ-5D-5L

For the changes from baseline at each visit in SF-36 eight subscale summary scores and three component summary scores / EQ-5D-5L visual analogue scale(VAS) and utility index scores, the same primary analysis method (MMRM) described in Section 8.2.1 will be analyzed.

Proportions of subjects with improvement of 30%, 50%, 70% and 90% at each visit compared to baseline in WOMAC pain subscale score, WOMAC physical function subscale score and PGA

A generalized linear mixed-effects model (GLMM) by logit type for response variable will be used to evaluate these binary response variables. The denominator degrees of freedom for the test statistics of estimated parameters will be approximated using the Kenward-Roger method. The estimated response rate for each treatment group and placebo group, P value, and 95% confidence interval of the odds ratio of each of the MT-5547 1 mg q4w and MT-5547 1 mg q8w groups compared to the placebo group in each binary response variables will be calculated at each visit using this GLMM approach.

- The covariates: baseline and the interaction of baseline and measurement time point.
- The fixed factors: Treatment group, measurement time point, the interaction of treatment group and measurement time point, K-L grade (2-3 or 4), and evaluated joint location (knee or hip)
- Random factors: Intercept for subject

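### The Protocol describes the PGA as a rating of change but its change from baseline is analysed; as coded, the Week 16 SAP's 90% PGA responder threshold cannot be reached

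*Protocol*

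**What the plan says.** **The instrument.** Protocol 9.2.3.1.2 calls the PGA "a measure whereby the patient assesses global improvement in osteoarthritis using the following 5-level scale". The levels run from Much improved (1), through Improved (2), No change (3) and Worse (4), to Much worse (5). It is collected on Attachment 6 at screening, at baseline and at visits after dosing.

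**The Protocol's endpoints and analysis.** Section 5.4.1 lists "Patient global assessment (PGA) (change from baseline at each assessment time point", and 10.1 repeats it. Section 13.3.2 (2) analyses "the change in the PGA from baseline to Week 16, the key secondary efficacy endpoint" in the same way as the primary endpoint. Section 13.3.2 (3) includes the PGA in its list of changes from baseline: "the WOMAC total score, PGA, the NRS score for the average pain on walking in the evaluated joint".

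**The SAPs.** Both list change from baseline in PGA as a secondary endpoint and analyse it by MMRM. Both tabulate baseline PGA in categories 1 to 5 with descriptive statistics (Week 16 SAP 8.1.3, Week 68 SAP 8.1.4).

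**Percent responders.** Week 16 SAP 8.2.3 plans a logit mixed model, with odds ratios, intervals and P values, at four levels of improvement: 30 and 50%, and then "70% and 90% at each visit compared to baseline in WOMAC pain subscale score, WOMAC physical function subscale score and PGA". Week 68 SAP 2.2.1 and 8.2.1 keep 90% for the two WOMAC scores but use only 30, 50 and 70% for the PGA.

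**OMERACT-OARSI.** Protocol 9.2.3.1.6: "The WOMAC pain subscore and physical function subscore and the PGA will be used to calculate the improvement rate". Week 16 SAP 7.1.2.7: "PGA is 1, 2, 3, 4 or 5, so the absolute change required for response is at least 1 point". Week 68 SAP 7.1.2.6 gives the same rule.

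**The concern.** A rating of change already contains the comparison with an earlier state. Subtracting a baseline rating from it has no clear meaning, and at screening or baseline the rating has no stated reference point. A score whose change from baseline is analysed has to be a rating of current state. One of the two descriptions is therefore wrong, and until it is settled a reader cannot say what a 1-point PGA improvement means.

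Two consequences follow. A high percent-improvement threshold may lie beyond what a five-point scale starting at 1 can show. And a 1-point drop may not match what the patient ticked, which would affect one of the three OMERACT-OARSI inputs.

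**Working it through.** **Inputs**

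- Codes 1 to 5: Week 16 SAP 7.1.2.7 and Week 68 SAP 7.1.2.6.
- Direction, 1 = best: the labels in Protocol 9.2.3.1.2, and nowhere else. The SAP sections give codes but no direction.
- Thresholds 30/50/70/90%: Week 16 SAP 8.2.3.
- OMERACT-OARSI PGA rule, a change of at least 1 point: the same SAP sections as the codes.

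The 90% is a chosen threshold, so there is no calculated figure of the plan to reproduce.

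**Step 1: which thresholds can be reached.** Let b be the baseline rating and v the visit rating. Improvement is 100 × (b − v)/b, largest at v = 1, where it equals 100 × (b − 1)/b.

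| Baseline b | Largest improvement | v reaching 30% | 50% | 70% | 90% |
|---|---|---|---|---|---|
| 1 | 0% | none | none | none | none |
| 2 | 1/2 = 50% | 1 | 1 | none | none |
| 3 | 2/3 = 66.7% | 1, 2 | 1 | none | none |
| 4 | 3/4 = 75% | 1, 2 | 1, 2 | 1 | none |
| 5 | 4/5 = 80% | 1, 2, 3 | 1, 2 | 1 | none |
| Pairs of 25 | | 8 | 6 | 2 | 0 |

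For a 1-to-k scale, (k − 1)/k ≥ 0.90 requires k ≥ 10. With no possible responder in any arm, the odds ratio cannot be estimated.

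**Step 2: dependence on direction.** If 5 were best, improvement would be 100 × (v − b)/b. Six of 25 pairs would then reach 90%: 1→2 (100%), 1→3 (200%), 1→4 (300%), 1→5 (400%), 2→4 (100%) and 2→5 (150%). Step 1 therefore needs 1 = best.

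**Step 3: the OMERACT-OARSI input, if the form carries the 9.2.3.1.2 labels.** Compare the SAP rule, b − v ≥ 1, with a visit rating of 1 or 2 (Much improved or Improved). This comparator is mine, not the documents'.

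| Baseline | v meeting the rule | Improved but missed | Credited but not improved | Disagreements of 5 |
|---|---|---|---|---|
| 1 | none | 1, 2 | none | 2 |
| 2 | 1 | 2 | none | 1 |
| 3 | 1, 2 | none | none | 0 |
| 4 | 1, 2, 3 | none | 3 (No change) | 1 |
| 5 | 1, 2, 3, 4 | none | 3 (No change), 4 (Worse) | 2 |

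The total is 2 + 1 + 0 + 1 + 2 = 6 of 25 pairs. These are possible combinations, not patients.

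**Step 4: the PGA MMRM.** The change v − b differs from v only by −1 × baseline at every visit. Baseline and baseline-by-time are covariates in the model (Week 16 SAP 8.2.1, Week 68 SAP 8.2.1), so they absorb that term. Treatment differences, standard errors and P values are identical whether v or v − b is modelled.

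**The case against.** The strongest reply is that the labels in 9.2.3.1.2 are a slip and the form is a state scale. The PGA is collected at screening and baseline, both SAPs tabulate it there, and every endpoint section uses change from baseline. The neighbouring WOMAC section has a comparable slip, naming osteoporosis where osteoarthritis is meant. This may well be right. The change-from-baseline analysis and the 1-point rule would then stand, and the labels would need correcting.

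It also weakens the 90% point. Direction rests on those same labels alone, and if they are wrong, direction is open too (Step 2). So a reader should not infer that 90% is unreachable whatever the form says. It is unreachable on the coding and direction as written. The Week 68 SAP's omission of 90% for the PGA fits this, but no reason is stated.

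The point is also small. The Week 16 SAP's endpoint list (2.2.1) has percent responders for pain and function only; the PGA enters in 8.2.3 through a threshold list shared by three measures. An empty 90% row is uninformative but would not mislead.

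Finally, part of the Week 16 errata is not visible, including replacement text for section 10. The visible entries do not mention the PGA, but a clarification elsewhere cannot be excluded.

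**Conclusion.** The concern holds in limited form. The contradiction between 9.2.3.1.2 and the endpoint and analysis sections is in the text and needs correcting whichever side is right. As written, one planned Week 16 responder analysis cannot return a result: the ceiling is 80% against a threshold of 90%, assuming codes 1 to 5 with 1 best.

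The OMERACT-OARSI part is conditional on Attachment 6. If the form carries the labels, the PGA input can be misclassified for some visit ratings when baseline is not 3.

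Three stronger readings are not supported:

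- That the PGA input is wrong for every patient whose baseline is not 3. In fact 19 of 25 pairs agree, and at each such baseline only 1 or 2 of the 5 ratings differ.
- That overall OMERACT-OARSI responders are wrong. The PGA is one of three inputs, the criteria diagram is not shown, and no baseline PGA distribution is given. The effect on the PGA input runs from none (all baselines 3) upward; the effect on overall response cannot be quantified.
- That the confirmatory results or the PGA treatment comparison are at risk. Protocol 13.3.2 (2) does name the PGA in its key secondary sentence, but H01 to H04 concern only WOMAC pain and physical function, and Step 4 shows the PGA MMRM differences do not move.

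Only secondary analyses are affected. The correction should still be made, because the PGA is a listed secondary endpoint and feeds another.

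**What to change.** 1. Check Attachment 6 for labels and direction, and reconcile Protocol 9.2.3.1.2 with Protocol 5.4.1, 10.1 and 13.3.2 and with both SAPs.
2. Delete the 90% PGA threshold from Week 16 SAP 8.2.3, as in the Week 68 SAP, unless the form shows that higher is better.
3. If the form is a rating of change, derive the OMERACT-OARSI PGA component from the post-baseline rating (for example 1 or 2, checked against the criteria diagram) and drop the PGA percent-improvement responders. The MMRM comparison needs no change.
4. If the form is a state scale, correct the labels in 9.2.3.1.2 and keep the change-from-baseline analysis and the 1-point rule.

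The cost is minor wording and, at most, derivation code, with no new data. In the rating-of-change case there is some loss of comparability with trials that use a state-type PGA.

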9.2.3.1.3 NRS (Average Daily Pain in the Evaluated Joint)

The (sub)investigator or a study support staff member will instruct the subject to use the IVRS every night between the start of the pre-treatment observation period and the day before Week 16 to report, using an 11-level NRS score (0 is no pain, to 10 is worst pain that is no longer thought about), the average pain on walking in the evaluated joint each day. Subjects who fail to report NRS data on 4 or more days during IVRS training in the pre-treatment observation period will not be allowed to advance to the treatment period (they will be considered ineligible to start the treatment period).

The (sub)investigator or a study support staff member will confirm that the subject is reporting the information using the IVRS correctly.

9.2.3.1.4 SF-36

The (sub)investigator or a study support staff member will ask the subject to fill out Attachment 7, "SF-36," at baseline, Weeks 4, 8, 16, 24, 32, 40, 48, and 68, and at treatment period discontinuation or post-treatment period observation period discontinuation, and will then collect Attachment 7 once the subject has filled it out. The (sub)investigator or a study support staff member will check the contents and if any revisions have been made will check the revisions that have been made by the subject and then enter the information in the case report form.

9.2.3.1.5 EQ-5D-5L

The (sub)investigator or a study support staff member will ask the subject to fill out Attachment 8, "EQ-5D-5L," at baseline, Weeks 4, 8, 16, 24, 32, 40, 48, and 68, and at treatment period discontinuation or post-treatment period observation period discontinuation, and will then collect Attachment 8 once the subject has filled it out. The (sub)investigator or a study support staff member will check the contents and if any revisions have been made will check the revisions that have been made by the subject and then enter the information in the case report form.

The EQ-5D-5L is a standardized measure of health status developed by the EuroQol group in order to provide a simple, generic measure of health for clinical and economical appraisal. The EQ-5D-5L descriptive system comprises the following 5 dimensions as measures of QOL: mobility, self-care, usual activities, pain/discomfort, and anxiety/depression. Each dimension has 5 levels, shown below.

1. No problems
2. Slight problems
3. Moderate problems
4. Severe problems
5. Unable/extreme

The respondent's overall health status is represented by a 5-digit number. The patient's health status as defined by these 5 parameters can be converted into a single numerical value that serves as the 5Q-5D-5L index score. A score of 1 indicates full health, and 0 means dead.

